To evaluate the impact of a novel TENS device on short term pain score during movement at day 1 post gynaecology surgery through a counterbalanced crossover trial: immediately, 1,2 and 4 hours after novel TENS application using a 0-10 Numerical Rating Scale (11 point NRS).

Primary outcome:

Pain score on movement immediately, 1, 2 and 4 hours (a total of 4 measures) after application of active-TENS vs sham-TENS sessions using 0-10 numerical rating scale (11 points NRS): higher score indicates greater pain.

Secondary outcomes:

- Repeated measures of the variance analysis for the serial pain scores across active-TENS vs sham-TENS sessions
- 2. Comparison of pain score on movement- immediately, 1, 2 and 4 hours after application of intervention or sham control sessions of 15 minutes after the first session only (across randomised arms).
- 3. Repeated measures of the variance analysis of the serial pain scores on movement (across randomised arms).
- 4. Identical analyses for similarly recorded blood pressure and pulse- immediately, 1, 2 and 4 hours after active-TENS vs sham-TENS sessions
- 5. Satisfaction score with the intervention immediately after the sessions, using 11 points NRS (higher score greater satisfaction)
- 6. Opioid consumption after application of active-TENS vs sham-TENS device

METHODOLOGY

Study design

This study will employ a randomized, triple-blind, placebo-controlled counterbalanced crossover trial design with 4 hours wash out period. This design allows each participant to serve as their own control, enhancing the reliability of the results as there is no control inter-subject variability at the same time minimising recruitment and outcome ascertainment bias.

Duration

18 months

Setting

Tertiary University Hospital, Gynaecology ward

Participants

The study population will consist of eligible and consented adult women at Day 1 post gynaecological surgery.

Inclusion criteria:

- Age ≥ 18 years old
- Patients undergoing elective or emergency gynaecology surgery (eg: myomectomy, hysterectomy, ovarian/ tubal surgeries) via transverse suprapubic incision under general anaesthesia
- Able to communicate in English or Malay
- Able to provide informed consent

Exclusion criteria:

- Contraindications to TENS (pacemaker, skin lesions)
- Chronic pain on regular opioids

Sample size

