- Using Power and Sample Size program, assuming a one-point difference in the 11 points-NRS pain score at each of the four assessment points of immediately after, 1, 2, and 4 hours to be clinically relevant, pain score standard deviation is uniformly at 2.5 at all assessment points, alpha 0.0125(Bonferroni correction for 4 primary outcomes) and power of 95%.
- We will need to study 110 pairs of results. Hence we intend to recruit 110 participants, each participant providing a pair of pain scores at each assessment point following crossover.
- The Bonferroni correction to the p value and the 95% power is statistically conservative, intended to reduce both Type 1 and 2 errors.

Randomization

- -Randomization will be performed using computerized sequence generator.
- -The sequence will be generated in random blocks of 4 or 8 (1:1 ratio) via https://www.sealedenvelope.com/simple-randomiser/v1/lists by a co-investigator not involved in the trial recruitment.
- -Participants will be assigned to one of two trial arms by opening a numbered, sealed, opaque envelope, with the lowest numbered envelope available assigned to the latest recruit.

ARM 1 : TENS followed by SHAM-CONTROL after a 4 hour gap

Or

ARM 2: SHAM-CONTROL followed by TENS after a 4 hour gap

Blinding

- Participants
- **Providers** administering the TENS or sham-controlled treatment first
- Assessors who will evaluate outcomes and collect the feedbacks

To minimize bias and control for placebo effect, a triple-blind design will be employed: 3rd person who is not the provider nor the assessor will control the frequency to be delivered.

TENS device

The Remedius ExStim Pro will be used to deliver external non-invasive stimulation through the Integrated Duo Stimulating Wand. The intervention will be administered by provider after undergoing training on device application by the investigator.

A sham-shock with frequency of 100Hz with amplitude 5mA will be delivered for 30s at the subumbilical region at the start of each session to further enhance the sham and blinding process. The TENS intervention will be delivered as follows:

TENS Parameters

Frequency: 100 Hz
 Pulse width: Medium
 Amplitude: 5 mA

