4. **Duration**: Two TENS devices will be used simultaneously, each targeting one site at a time. Each site will be treated for 5 minutes, with two sites treated simultaneously. This will be repeated for 3 rounds, ensuring all 6 application sites are covered, requiring a total duration of 15 minutes per session.

Timing of Intervention:

The TENS intervention will be initiated on Day 1 (morning after) post gynaecology surgeries.

Intervention protocol

TENS First: Participants will receive TENS therapy at a frequency of 100 Hz and 5 mA intensity (set at medium pulse width). The TENS device will be applied at 6 fixed points for 5 minutes each, 1-2 cm lateral to wound edge and 1-2 cm above along, covering the transverse suprapubic incision. After 4 hours wash out, the same TENS device will be used in exactly the same manner with output at sham setting 0 Hz and 0 mA intensity.

[figure not shown]
Control(Sham) First: Participants will receive sham-control TENS therapy with output setting 0 Hz and 0 mA intensity. The TENS device will be applied at 6 fixed points for 5 minutes each, 1-2 cm

VERSION NO:1 VERSION DATE: 15th July 2025

lateral to wound edge and 1-2 cm above along, covering the transverse suprapubic incision. After 4 hours wash out, participants will receive TENS therapy at a frequency of 100 Hz and 5 mA intensity (set at medium pulse width).

[figure not shown]
At the start of both sessions, TENS at a frequency of 100 Hz and 5 mA intensity will be delivered to the subumbilical region, briefly for 30 seconds only to generate a TENS sensation and enhance the sham. If the sensation cannot be tolerated, participation will be stopped.

Participants will still receive standard of care analgesics post gynaecology surgery while undergoing

-the devices will be given by provider who are trained by the investigator (they will undergo training on device application and trial process

Prong application points

Data Analysis:

- Data will be entered into SPSS(Version 27, IBM, SPSS Statistics)
- T-test will be used to analyse mean for normally distributed data
- Mann-Whitney U test for non-normally distributed or ordinal data
- Chi-square test (with Fisher exact test if ≥20% of evaluated have expected cell size number
 5) for categorical data
- Analysis will be on intention-to-treat basis
- Two-sided p-values were reported and p<0.0125 regarded as significant for four primary outcome and p < 0.05 for all other analyses

RESEARCH DATA

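### Participant blinding is not credible as designed and no listed outcome tests it, although the primary outcome is each woman's own pain rating

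*Protocol*

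**What the plan says.** Under Blinding, the protocol names participants, providers and assessors as blinded and gives the purpose: "To minimize bias and control for placebo effect, a triple-blind design will be employed". A third person, neither provider nor assessor, sets the output.

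Under Intervention protocol, both sessions begin alike: "At the start of both sessions, TENS at a frequency of 100 Hz and 5 mA intensity will be delivered to the subumbilical region". The protocol gives the length and aim of this burst as "briefly for 30 seconds only to generate a TENS sensation and enhance the sham". The protocol expects this current to be felt, since it adds: "If the sensation cannot be tolerated, participation will be stopped".

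After the burst the sessions part. Active treatment is 100 Hz and 5 mA at medium pulse width over six points beside the wound, "requiring a total duration of 15 minutes per session". For the sham, "the same TENS device will be used in exactly the same manner with output at sham setting 0 Hz and 0 mA intensity". Every woman receives both, in randomised order, with a 4-hour gap.

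The primary outcome is "Pain score on movement immediately, 1, 2 and 4 hours (a total of 4 measures) after application of active-TENS vs sham-TENS sessions", on a 0-10 numerical rating scale. The secondary outcomes include a comparison of pain scores after the first session only, across randomised arms. No listed outcome records which session the woman believed was active.

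**The concern.** A 0-10 pain score is the woman's own rating, so she is the person whose blinding matters most for the primary outcome. The third person can conceal the setting from provider and assessor but cannot conceal what she feels. Her blinding therefore rests on the 30-second burst, which gives both sessions the same opening but leaves the following 15 minutes different. In a crossover she can also compare the two sessions directly within a few hours.

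If many women recognise the sessions, expectation can enter the pain score, the satisfaction score and opioid requests. A positive result could then not be separated from a response to a recognised session, which is what the sham was meant to rule out. A larger sample would not remove such a bias. A treatment guess that is not asked at the bedside cannot be recovered in the analysis.

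**Working it through.** **Step 1. Compare the two sessions (Protocol, TENS device and Intervention protocol).**

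| Element | Active session | Sham session |
|---|---|---|
| Opening burst, subumbilical | 100 Hz, 5 mA, 30 s | 100 Hz, 5 mA, 30 s |
| Six wound-edge points, 15 min | 100 Hz, 5 mA | 0 Hz, 0 mA |
| Total time with current | 30 + 15 × 60 = 930 s | 30 + 0 = 30 s |

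For the whole 15 minutes the sessions differ in a current of the frequency and amplitude that the protocol itself uses to produce a sensation. The match is established for frequency and amplitude only: the burst's pulse width is not stated, and the burst is given at a different site.

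**Step 2. Reproduce the planned sample size.** Inputs from Sample size and Data Analysis: difference 1 point, SD 2.5, alpha 0.0125 two-sided, power 95%, 110 pairs.

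- Normal approximation: n = (SD × (z₁₋α/₂ + z_power) / difference)² = (2.5 × (2.498 + 1.645) / 1)² ≈ 107.3, rounded up to 108.
- Noncentral t: 111 pairs; power at 110 pairs is 94.9%.

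The stated 110 is reproduced if 2.5 is read as the SD of the paired difference. That reading is used below.

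**Step 3. Find the smallest significant difference.** Standard error = 2.5 / √110 = 0.238. The two-sided critical t at 0.0125 with 109 degrees of freedom is about 2.54. The product is about 0.61 points. Any observed mean difference larger than this is significant if the SD is as planned, and it lies below the 1-point target.

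**Step 4. Illustrate the effect of a bias.** Assume that TENS has no true effect and that recognition shifts the mean active-minus-sham score by b points. The chance of a significant result at one time point is P(|T| > 2.54), where T is noncentral t with 109 degrees of freedom and noncentrality b / 0.238.

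| Assumed mean bias b | Chance of significance per time point |
|---|---|
| 0 | 1.25% |
| 0.1 | 2.0% |
| 0.25 | 7.2% |
| 0.5 | 33.4% |
| 0.75 | 72.7% |

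The protocol gives neither a recognition rate nor a shift, so every value of b is an assumption. For scale, 0.25 would arise if half the women recognised the sessions and recognition moved their difference by 0.5 points (0.5 × 0.5). The table shows how sensitive the test is to a bias, not that one exists.

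**Step 5. See what the first-session comparison offers.** It comes before any woman has met the other condition, so it removes the session-to-session contrast. The burst still precedes it and remains a reference. It is also less precise: with about 110 / 2 = 55 women per arm, and if 2.5 were also the SD of a single score, its standard error would be 2.5 × √(2/55) = 0.477, twice the 0.238 of the paired comparison.

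**The case against.** A reader might infer that the women are certainly unblinded. The documents do not support that. They give no recognition rate and nothing on how 5 mA feels beside a fresh incision, where sensation may be reduced. The burst is also at another site. This stands, and it is why the point is that blinding is not credible and is untested, rather than that it has failed.

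Nor do the documents show that the burst makes recognition worse. Without it the sham session would contain no current at all. What can be said is that the burst does not mask the next 15 minutes.

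It is tempting to say that the bias always favours active TENS. That is likely but not certain: the protocol itself foresees women who cannot tolerate the sensation, and discomfort could push some ratings the other way.

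The plan has partial protection. The first-session comparison removes the direct contrast between sessions, and blood pressure and pulse are not self-rated. Both stand, but these are secondary outcomes, and the pain ratings after the first session still follow a burst.

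Finally, what women are told about sensation would normally be in the participant information, which is not at hand, so no missing script can be charged to the plan. The missing treatment guess is different: it is data to be collected, and the outcome list does not contain it.

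**Conclusion.** The concern holds in this form. The protocol's stated participant blinding is not credible, because a current the protocol treats as perceptible is present for 15 minutes in one session and absent in the other, in the same woman, about 4 hours apart. No listed outcome would show whether the blinding held.

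The size of the resulting bias is unknown and most likely, though not certainly, favours active TENS. Under the assumptions of 110 pairs, paired-difference SD 2.5, two-sided alpha 0.0125 and no true effect, a mean bias of 0.25 or 0.5 points would produce about 7% or 33% false positives per time point. These are illustrations, not estimates. The sample size itself reproduces and is not in question here.

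**What to change.** 1. After the last pain score, 4 hours after session 2, ask each woman which session she thinks was active (first, second, don't know) and why (felt current, pain relief, other). At that point the question cannot alter any pain score. Report the answers descriptively by arm, with a blinding index.
2. Reword the blinding claim to provider- and assessor-blind, sham-controlled, with participant masking attempted and assessed. State that a positive self-rated result may include expectation effects if most women identify the sessions.
3. Report the already planned first-session comparison between arms beside the primary result as supportive evidence, noting that the burst is a reference there too and that the comparison is less precise.

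Do not make attribution to TENS depend on the women who guessed wrong or did not know. The guess comes after treatment and is influenced by real relief, so that subgroup is selected against benefit.

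The cost is one question at an existing contact, a short amendment and a less favourable blinding claim. A guess at the end of the study can partly reflect pain relief; asking the reason helps to interpret it but does not remove the problem. No stimulation setting changes.

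### The Data Analysis section names Mann-Whitney U, and a t-test of unstated type, but no paired or crossover test for a primary comparison sized on 110 within-woman pairs

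*Protocol*

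**What the plan says.** The protocol describes a two-period crossover in which each woman is her own control. The primary outcome is pain on movement (0-10 NRS) immediately and 1, 2 and 4 hours after active versus sham sessions.

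The Sample size section is explicitly paired: "We will need to study 110 pairs of results", with "each participant providing a pair of pain scores at each assessment point following crossover". Its inputs are "assuming a one-point difference in the 11 points-NRS pain score at each of the four assessment points", "pain score standard deviation is uniformly at 2.5 at all assessment points" and "alpha 0.0125(Bonferroni correction for 4 primary outcomes) and power of 95"%.

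The Data Analysis section then lists tests by type of data and does not map them to outcomes:
- "T-test will be used to analyse mean for normally distributed data"
- "Mann-Whitney U test for non-normally distributed or ordinal data"
- chi-square or Fisher exact for categorical data.

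The same list sets the primary threshold: "Two-sided p-values were reported and p<0.0125 regarded as significant for four primary outcome".

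Repeated-measures analysis of variance appears only among the secondary outcomes: item 1 for active versus sham sessions, and item 3 across randomised arms. Secondary outcome 2 compares the randomised arms after the first session only.

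**The concern.** Mann-Whitney U assumes two independent samples and has no paired version. An 11-point NRS is commonly classed as ordinal and may well be non-normal, so the protocol's own rule plausibly sends the primary outcome to that test. The list also carries the 0.0125 threshold, so it is evidently meant to cover the four primary comparisons.

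In this trial the active and sham scores come from the same woman. An independent-sample test computes its standard error as if they came from different women and so ignores the within-woman correlation. With positive correlation that standard error is too large, and a real one-point effect can be missed in a trial that was planned to detect it with 95% power. The parts of the protocol also disagree: the sample size presumes a pairing that no listed primary test is stated to use.

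**Working it through.** **Inputs from the protocol.** Difference 1 point; SD 2.5; alpha 0.0125, two-sided; power 95%; 110 pairs. The protocol does not say whether 2.5 is the SD of scores or of within-woman differences, and it gives no within-woman correlation ρ. Both SD readings are therefore shown, with ρ assumed at 0, 0.3, 0.5 and 0.7.

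**Step 1: reproduce the 110.** Take 2.5 as the SD of differences in the paired formula n = [SD × (z for alpha + z for power) / difference]².
- Normal quantiles: [2.5 × (2.498 + 1.645)]² = 107.3, so 108.
- Iterated with t quantiles: 110.2.
- Exact noncentral-t power of a paired t-test at n = 110: 94.9%.

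The stated size is thus reproduced as a two-sided paired calculation. Variants that do not give it:
- one-sided paired: 94.4, so 95 pairs;
- two independent groups: 2 × 107.25 = 214.5, so 215 per group.

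**Step 2: standard errors.** Let s be the SD of scores. The SD of differences is s√[2(1−ρ)].
- True SE of the mean difference: s√[2(1−ρ)/110].
- SE used by an independent-sample t-test: s√(2/110).
- Ratio of used to true SE: 1/√(1−ρ).

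**Step 3: type I error of the unpaired t-test.** The critical value is 2.519 (218 df). The actual two-sided error is about 2Φ(−2.519/√(1−ρ)), whichever SD reading applies.
- ρ = 0.3: 2Φ(−3.01) = 0.0026
- ρ = 0.5: 2Φ(−3.56) = 0.0004
- ρ = 0.7: 2Φ(−4.60), below 0.0001

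All are below the nominal 0.0125.

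**Step 4: power of the unpaired t-test.** Power is about Φ[(1 − 2.519 × used SE) / true SE]. Worked example at ρ = 0.5, s = 2.5: used SE 0.337, true SE 0.238, so Φ[(1 − 0.849)/0.238] = Φ(0.63) = 74%.

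| ρ | 2.5 is SD of differences: paired / unpaired | 2.5 is SD of scores: paired / unpaired |
|---|---|---|
| 0 | 94.9% / 95% | 67% / 67% |
| 0.3 | 94.9% / 88% | 84% / 70% |
| 0.5 | 94.9% / 74% | 94.9% / 74% |
| 0.7 | 94.9% / 34% | >99% / 79% |

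Simulation of normal scores agrees with the unpaired figures to within about one percentage point.

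**Step 5: Mann-Whitney itself.** Simulation of rounded 0-10 scores (SD of scores 2.5, means one point apart, 3,000 replicates per scenario) gave:

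| ρ | Mann-Whitney | Signed-rank | Paired t |
|---|---|---|---|
| 0.3 | 66% | 81% | 82% |
| 0.5 | 69% | 93% | 94% |
| 0.7 | 73% | >99% | >99% |

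With no true difference and ρ = 0.5, Mann-Whitney rejected in about 0.07% of trials against a nominal 1.25%.

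Within each row, only the gap between paired and unpaired is due to the choice of test. Where paired power is itself below 95% (SD of scores, ρ below 0.5), that shortfall is a separate sample-size matter that follows from the undefined SD.

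**The case against.** Several points on the other side have weight.

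- **The t-test may be paired.** A reader might infer that the protocol prescribes an independent-sample t-test. It does not say so. Read with the paired sample size, a paired t-test is at least as plausible, and planning on a mean difference with an SD suggests that the NRS might be analysed as a mean. This stands: the t-test is unspecified, not wrong. It does not rescue Mann-Whitney U, which cannot be paired.
- **The list is generic.** Both tests, in independent form, suit the first-session comparison across arms. This also stands, so the protocol does not actually state that 110 active and 110 sham scores will be handled as 220 separate women. But nothing confines the tests to that comparison, and if they were so confined, the primary comparison would have no stated test.
- **The pairing is not abandoned everywhere.** Secondary outcome 1 plans a repeated-measures analysis of active versus sham. That is true, so it would be too strong to say that the crossover is defeated. It is nonetheless secondary and does not supply the four primary tests.
- **The error is conservative.** With positive correlation there is no inflation of type I error and no added risk of a false claim of benefit. What remains is the risk of a false negative.
- **A SAP could settle it.** Whether the t-test is paired could be left there. Mann-Whitney U for ordinal data, however, is a rule the protocol states, and a SAP naming another test would conflict with it.

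**Conclusion.** Wrong as written for ordinal or non-normal data, and unspecified for normal data. The primary contrast and sample size are within-woman; the only test named for ordinal data is not, and no paired or crossover test is named for the primary comparison.

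The consequence is conditional on an independent-sample test being applied to that comparison. No single loss figure can be quoted, because it turns on ρ and on the meaning of 2.5. For ρ from 0 to 0.7, the t-test loss runs from none to about 61 percentage points (94.9% to 34%) if 2.5 is the SD of differences, and from none to roughly 20 points if it is the SD of scores. A drop to 74% is the value at ρ = 0.5, not a property of the plan.

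The documents do not support reading this as an inadequate sample size in itself: 110 pairs is right for a paired test if 2.5 is the SD of differences.

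**What to change.** 1. For all active-versus-sham comparisons (pain, blood pressure and pulse, satisfaction, opioid consumption), prespecify one paired analysis as the main one. For the primary outcome, preferably fit a linear mixed model at each of the four time points, with treatment, period and sequence effects and a random participant effect, tested at 0.0125. A paired t-test is the simpler alternative. The period term is worth having because post-operative pain is likely to change between two sessions hours apart on the same day.
2. Replace Mann-Whitney U with the Wilcoxon signed-rank test wherever ordinal or non-normal active-versus-sham data are compared, and say in advance whether the NRS is treated as a mean or as ordinal.
3. Keep the independent t-test and Mann-Whitney U only for the first-session comparisons across randomised arms, and say so.
4. In the Sample size section, state whether 2.5 is the SD of scores or of within-woman differences. If it is the SD of scores, give the assumed correlation.

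The cost is a few lines of text. No new data are needed, recruitment is unaffected if 2.5 is confirmed as the SD of differences, and SPSS provides these procedures. The change should be made before the data are analysed, so that the test is not chosen with results in view.

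### Holm's procedure could replace plain Bonferroni for the four primary pain tests: same 5% family-wise error, some extra power, and an improvement rather than the repair of an error

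*Protocol*

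**What the plan says.** The primary outcome (Protocol, Objectives/Outcomes) is "Pain score on movement immediately, 1, 2 and 4 hours (a total of 4 measures") after active versus sham TENS, so there are four primary tests.

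The Sample size section uses "alpha 0.0125(Bonferroni correction for 4 primary outcomes) and power of 95" per cent, "assuming a one-point difference in the 11 points-NRS pain score at each of the four assessment points", and "pain score standard deviation is uniformly at 2.5 at all assessment points". It arrives at 110 pairs and adds: "The Bonferroni correction to the p value and the 95% power is statistically conservative".

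Data Analysis repeats the threshold: "p<0.0125 regarded as significant for four primary outcome and p < 0.05 for all other analyses".

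Secondary outcome 1 is "Repeated measures of the variance analysis for the serial pain scores across active-TENS vs sham-TENS sessions". As a secondary outcome it falls under the 0.05 clause. The protocol states no testing order and no dependence on the primary result.

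**The concern.** Bonferroni compares every p-value with 0.05/4, however many of the other hypotheses have already been rejected. Holm relaxes the threshold after each rejection and still holds the family-wise error at 5% under any dependence between the tests. Whatever Bonferroni rejects, Holm rejects too. The sample size assumes a real one-point effect at all four times, and that is the setting in which the later, relaxed steps help most. What is at stake is a few points of power per time point, and more if the investigators hope to show an effect throughout the four hours.

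There is a smaller, related matter. The repeated-measures ANOVA in secondary outcome 1 uses the same scores, participants and contrast as the primary tests, but is judged at 0.05. If no time point passes its corrected test, a significant ANOVA could still be reported as evidence that TENS reduces pain.

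**Working it through.** **Inputs from the protocol:** four primary tests; 0.0125 per test, two-sided; difference 1 point at each time; SD 2.5; 95% power; 110 pairs.

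**Assumptions:** 2.5 is the SD of the paired difference; paired t-tests; equal correlation between the four time-point differences, at 0, 0.5 or 0.8, because the protocol gives none.

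**1. The plan's own figure.** With n = [(z for 1 − 0.0125/2 + z for 0.95) × SD / difference]²:

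- Normal approximation: [(2.498 + 1.645) × 2.5 / 1]² = 107.3, so 108.
- The same formula with t quantiles, iterated on n − 1 degrees of freedom: 110.2.
- Exact power at n = 110 from the noncentral t: 94.9%.

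The stated 110 pairs is reproduced. The independent-groups formula gives 215 per arm and does not reproduce it.

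**2. Error control of the stated rule.** 4 × 0.0125 = 0.05, so the primary family is controlled. If the tests were independent the family-wise error would be 1 − (1 − 0.0125)⁴ = 4.9%.

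**3. Holm thresholds.** Order the four p-values from smallest to largest and compare them with 0.05/4 = 0.0125, 0.05/3 = 0.0167, 0.05/2 = 0.025 and 0.05/1 = 0.05, stopping at the first failure. The first step is the Bonferroni step. The chance of at least one rejection is therefore the same under both rules.

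**4. Power with one point at all four times.** Simulation of four correlated paired t-tests, n = 110, SD of differences 2.5, 40,000 runs per scenario:

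| Correlation | Per time point, Bonferroni → Holm | All four, Bonferroni → Holm | At least one, both rules |
|---|---|---|---|
| 0 | 95% → 98% | 81% → 94% | 100% |
| 0.5 | 95% → 98% | 85% → 95% | 99.7% |
| 0.8 | 95% → 97% | 89% → 96% | 98.8% |

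The gain for all four is 13, 10 and 7 points.

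**5. Power when fewer effects are real (correlation 0.5).** With an effect at one time only, power there is 95% under both rules. With effects at two times it is about 95% against 96% at each.

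**6. Type I error.** With no effect at any time, either rule makes at least one false rejection in 4.8/4.2/3.2% of trials (correlation 0/0.5/0.8). With two real and two null effects (correlation 0.5), the rate is 2.3% for Bonferroni and 4.2% for Holm. Holm uses error that Bonferroni leaves unspent and stays below 5%.

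**7. The ANOVA at 0.05.** The active-versus-sham treatment effect equals a t-test on each participant's mean difference over the four times. With no effect anywhere:

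| Correlation | Any primary test at 0.0125 | Any primary test, or ANOVA at 0.05 | Excess |
|---|---|---|---|
| 0 | 4.8% | 8.6% | 3.8 points |
| 0.5 | 4.2% | 6.5% | 2.3 points |
| 0.8 | 3.2% | 5.4% | 2.2 points |

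Repeat simulations moved these null figures by up to half a point; one gave 5.0/4.5/3.4% and 8.9/7.0/5.5%. In each, the excess is about 2 to 4 points.

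**The case against.** The strongest reply is that nothing here is wrong. Bonferroni is prespecified and valid, is used consistently in Sample size and Data Analysis, and the planned 95% power per time point is already net of the correction. It also has simple matching simultaneous confidence intervals, which Holm lacks. The larger Holm gains apply to winning all four time points, which the protocol never requires. All of this stands, and it is why the point is an option to improve the plan. It does not remove the fact that, for the tests themselves, Holm rejects at least as often at the same error rate, in exactly the scenario the sample size assumes.

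On the ANOVA, the reply is that it is labelled secondary, that uncorrected secondary tests are common, and that the statistical analysis plan, which is not shown, may already call it supportive. This also largely stands. The combined rates in the last table pool a primary family with a secondary test, and the protocol does not undertake to control that error. What remains is that the protocol's stated rule lets this re-test of the same contrast be called significant with no reference to the primary result.

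**Conclusion.** The point holds as a cheap improvement of low severity. Under the plan's own assumption of one point at every time, Holm adds about 2 to 4 points of power per time point and 7 to 13 points for all four. It adds nothing to the chance of at least one success and almost nothing if only one effect is real. The figures rest on the assumed correlations and on reading 2.5 as the SD of the paired difference, which is the reading that reproduces 110. That Holm never rejects less rests on neither.

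A reader might infer two stronger things that the document does not support:

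- **That the Bonferroni rule is a mistake or leaves the trial short of power.** It is valid, it matches the sample size, and it gives 94.9% power per test at 110 pairs. A larger SD of differences would widen Holm's advantage, but the protocol gives no such figure.
- **That the 0.05 ANOVA defeats the correction.** The primary family's error stays at or below 5% whatever the secondary tests show, and nothing in the protocol says the ANOVA can rescue failed primary tests. The real exposure is over-reading: an isolated significant ANOVA in about 2 to 4% of trials when TENS has no effect.

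**What to change.** In Data Analysis, replace the fixed 0.0125 threshold for the primary outcome with Holm's procedure over the four time points: ordered p-values against 0.0125, 0.0167, 0.025 and 0.05, stopping at the first that fails. Keep the sample size calculation at 0.0125, which is the first Holm step.

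State which confidence intervals will accompany the tests, for example unadjusted 95% intervals labelled as such. This is the one small cost, since Holm has no simple matching intervals.

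Add one sentence saying that the repeated-measures ANOVA of the same active-versus-sham pain scores is supportive and cannot establish a TENS effect when no Holm-adjusted primary test is significant.

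The change is to text only. Recruitment, conduct and data collection are unaffected. It should be made before unblinding, because a later switch would look post hoc.
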